##### **Serious/Non-Serious**

AEs that meet the criteria specified in [Section 9.2.8.1](#) are to be considered serious.

##### **Relationship to Study Drug**

The relationship of each AE to study drug is to be assessed by the Investigator according to categories in Table 5.

**Table 5: Criteria for Determination of Adverse Event Relationship to Study Drug**

AE (is):	Relationship Between Study Drug and AE:				
	None	Unlikely	Possibly	Likely	Definitely
Clearly the result of an external factor	Yes	No	No	No	No
Probably/possibly the result of another factor	No	Yes	Yes	No	No
Has a chronological relationship with the time of administration and/or represents a known reaction to Study Drug	No	No	Yes	Yes	Yes
Disappears or decreases after discontinuation of the Study Drug	NA	NA	NA	Yes	Yes
Recurs on renewed administration (re-challenge)	No	No	NA	NA	Yes or NA**

\*\*A re-challenge is not required; if done, re-challenge would be expected to be positive.  
NA = not applicable

## Intensity

The intensity of each AE is to be assessed by the Investigator according to the NCI CTCAE, version 4.03. If the AE is not included in the NCI CTCAE, version 4.03, then the Investigator is to determine the intensity of the AE according to the following criteria:

- Mild (Grade 1): Asymptomatic or mild symptoms: clinical or diagnostic observations only; intervention not indicated.
- Moderate (Grade 2): Minimal, local, or non-invasive intervention indicated; limited age-appropriate instrumental activities of daily living.
- Severe (Grade 3): Severe or medically significant but not immediately life threatening; hospitalization or prolongation of hospitalization indicated; disabling; limiting self-care activities of daily living; incapacitating with inability to work or perform normal daily activity.
- Life-threatening (Grade 4): consequences: urgent intervention indicated.
- Death (Grade 5) related to an AE.

### 9.2.8.3. Recording Adverse Events

All AEs occurring from the time written informed consent is obtained through the Day 100 ( $\pm 7$  days) visit are to be recorded in the source documents and in the eCRF. AEs will be documented as occurring pre-conditioning (i.e., pre-tinostamustine); during conditioning (i.e., after the start of the first tinostamustine infusion through immediately before the start of ASC infusion); or after ASCT (i.e., after the start of ASC infusion). All AE reports are to contain the following details regarding the AE: a brief description, onset date, duration, intensity, treatment required, relationship to study drug, study drug action taken, outcome, and whether the event is classified as serious.

### 9.2.8.4. Reporting Serious Adverse Events

SAEs will be collected and recorded throughout the study period, beginning with the signing of the informed consent form (ICF) through the Day 100 ( $\pm 7$  days) visit, or after the end of the study if thought to be related to study drug.

The Investigator must report all SAEs to the Sponsor within 24 hours of discovery.

A completed SAE report is to be sent to the Medical Monitor's attention within 24 hours of discovering the event. The initial report should include at least the following information:

- Patient's ID number;
- Description and date of the event;
- Criterion for serious; and

- Preliminary assignment of causality to study drug.

The Medical Monitor will contact the Investigator via telephone for follow-up information regarding the SAE, as appropriate.

The Investigator, or designated party, should notify the appropriate IRB/EC of SAEs occurring at the study center and other AE reports received from the Sponsor, in accordance with local procedures and statutes.

SAEs that are considered as possible or probably related to the investigational product, and as unexpected (i.e., SUSARs), will be reported to the concerned Competent Authorities (CAs) and IRBs/ECs by the Sponsor or Sponsor's designee as required by applicable local regulations. Per regulation, any fatal or life-threatening SUSAR will be reported to the CAs/IRBs/ECs within 7 calendar days, and additional information within an additional 8 calendar days. The Sponsor or Sponsor's designee is required to submit any other SUSAR to the CAs/IRBs/ECs within 15 calendar days of notification. The Sponsor or its designee is also responsible for notifying the investigational sites of all expedited SAEs. The Investigator must keep copies of all expedited SAE information including correspondence with the Sponsor on file.

#### **9.2.8.5. Follow-Up of Adverse Events**

The Investigator must continue to follow all SAEs and non-serious AEs considered to be at least possibly related to study drug either until resolution or the Investigator assesses them as chronic or stable. This follow-up may extend after the end of the study.

#### **9.2.8.6. Reporting Safety Information**

The Investigator must promptly report to his or her IRB/EC all unanticipated problems involving risks to patients. This includes death from any cause and all SAEs reasonably or possibly associated with the use of Study Drug according to the IRB/EC's procedures.

The Sponsor will assess the severity and frequency of adverse drug reactions in adults versus pediatric patients, and will submit findings annually in the Development Safety Update Report/Annual Report.

#### **9.2.8.7. Protocol Deviations Due to an Emergency or Adverse Event**

Departures from the protocol will be determined as allowable on a case-by-case basis and only in the event of an emergency. The Investigator or other physician in attendance in such an emergency must contact the Medical Monitor as soon as possible to discuss the circumstances of the emergency.

The Medical Monitor, in conjunction with the Investigator, will decide whether the patient should continue to participate in the study. All protocol deviations and reasons for such deviations must be noted in the eCRF.

### **9.2.8.8. Pregnancy**

Pregnancy is considered unlikely in this study, given the population of patients to be enrolled. Nonetheless, pregnancies occurring within 12 months after the patient's last dose of tinostamustine will not be considered serious, but are to be reported using the same procedures as for SAEs described in [Section 9.2.8.4](#).

The patient is to be referred to an obstetrician/gynecologist experienced in reproductive toxicity for further evaluation and counseling.

The Investigator will follow the patient until completion of the pregnancy, and must notify the Medical Monitor of the outcome within 5 days. The Investigator will provide this information as a follow-up to the initial report.

If the outcome of the pregnancy meets the criteria for immediate classification as an SAE (i.e., spontaneous abortion [any congenital anomaly detected in an aborted fetus is to be documented], stillbirth, neonatal death, or congenital anomaly), then the Investigator should report it as such. Furthermore, all neonatal deaths that occur within 30 days of birth are to be reported, without regard to causality, as SAEs. In addition, any infant death after 30 days that the Investigator suspects is related to the *in utero* exposure to tinostamustine should also be reported.

## **9.3. Disease Assessments**

### **9.3.1. Myeloma Protein Measurements in Serum and Urine**

#### **9.3.1.1. Serum**

Blood samples for quantitation of immunoglobulin (Ig) (IgA, IgG, and IgM are required; IgD and IgE are optional) and M-protein and assessment of M-protein by immunofixation in serum are to be collected from all patients at the time points designed in [Table 1](#). Note that in the case of IgA MM, MM IgA values should be used.

All samples will be analyzed by the local laboratory. Assessments of response will be evaluated by two independent reviewers.

#### **9.3.1.2. Urine**

Twenty-four hour urine samples for quantitation of M-protein and assessment of M-protein by immunofixation are to be collected from all patients during Screening. For patients with positive findings at Screening, such samples also are to be collected at the time points designed in [Table 1](#). Patients with negative Screening results need not provide urine samples for M-protein quantitation and assessment after Screening.

All samples will be analyzed by the local laboratory. Assessments of response will be evaluated by two independent reviewers.

### **9.3.2. Free Light Chain Testing**

Serum samples for free light chain (FLC) testing are to be collected from all patients during Screening and at the time points designed in [Table 1](#). The free kappa/lambda ratio is to be recorded in the eCRF.

A serum sample for FLC testing also is to be collected in order to confirm stringent complete response (sCR).

### **9.3.3. Bone Marrow Examination**

Bone marrow aspiration to be performed for all patients during Screening, and for patients who achieve a CR, on Day 100 ( $\pm 7$  days) post-ASCT. Bone marrow aspiration and biopsy are to be repeated during treatment as clinically indicated.

Approximately 5mL of the same sample (i.e., “first-pull”), collected in ethylenediaminetetraacetic acid (EDTA) tubes, will be used for assessment of MRD-N using next-generation flow cytometry.

### **9.3.4. Skeletal Survey and Other Imaging Studies**

Skeletal surveys (plain radiographs, or any other method used as standard care at the site, of the skull, spine, ribs, pelvis, humeri and femora) are to be performed during Screening. If a skeletal survey has been performed within 3 months before Baseline, then this evaluation need not be repeated during Screening.

A skeletal survey is to be repeated during the study as clinically indicated.

Other appropriate imaging studies (e.g., magnetic resonance imaging, CT, X-ray) to evaluate the patient’s disease are to be performed during Screening per standard of care, as determined by the Investigator. Appropriate imaging studies are to be repeated as necessary to confirm CR.

### **9.3.5. Assessment of Disease Response**

The Investigator will perform tests that will allow evaluation of response to therapy according to the IMWG Criteria, as outlined in Table 6. Patients who are determined to have CR are then to have additional tests performed that will allow further characterization of the CR.

Assessment of disease response using non-invasive procedures will be performed at the time points designed in [Table 1](#). Appropriate imaging studies and bone marrow aspirates/biopsies must be repeated only in patients suspected of having a CR, based on non-invasive procedures.

**Table 6: IMWG Response Criteria**

Response	IMWG Criteria
Complete response (CR) 	

• Negative immunofixation of serum and urine, and

• Disappearance of any soft tissue plasmacytomas, and

• <5% plasma cells in bone marrow

*Mundipharma-EDO GmbH  
Clinical Study Protocol EDO-S101-1004  
Version 2.0, 18 June 2018*

Response	IMWG Criteria
Stringent complete response (sCR)	CR as defined above plus 

• Normal FLC ratio, and

• Absence of clonal plasma cells (PC) by immunohistochemistry or 2-4 color flow cytometry.

Immunophenotypic CR	Stringent CR plus 

• Absence of phenotypically aberrant PC (clonal) in bone marrow (BM) with a minimum of one million of total BM cells analyzed by multiparametric flow cytometry (with >4 colors)

Molecular CR	CR plus 

• Negative allele-specific oligonucleotide-polymerase chain reaction (ASO-PCR), sensitivity <math>10^{-5}</math>

Very good partial response (VGPR) 	

• Serum and urine M-component detectable by immunofixation but not on electrophoresis, or

• <math>\geq 90\%</math> or greater reduction in serum M-component plus urine M component <math>< 100</math> mg per 24 hours

Partial response (PR)	

• <math>\geq 50\%</math> reduction of serum M-protein and reduction in 24-h urinary M-protein by <math>\geq 90\%</math> or to <math>< 200</math> mg per 24 hours

• If the serum and urine M-protein are unmeasurable a <math>\geq 50\%</math> decrease in the difference between involved and uninvolved FLC levels is required in place of the M-protein criteria

• If serum and urine M-protein are unmeasurable, and serum free light assay is also unmeasurable, <math>\geq 50\%</math> reduction in bone marrow plasma cells is required in place of M-protein, provided baseline percentage was <math>\geq 30\%</math>

• In addition to the above criteria, if present at Baseline, <math>\geq 50\%</math> reduction in the size of soft tissue plasmacytomas is also required

Stable disease (SD)	Not meeting criteria for CR, VGPR, PR or progressive disease.

Response	IMWG Criteria
Progressive disease (PD) 	

• Increase of 25% from lowest response value in any one or more of the following:

• Serum M-component (absolute increase must be <math>\geq 0.5</math> g/dL) and/or

• Urine M-component (absolute increase must be <math>\geq 200</math> mg/24 hours) and/or

• Only in patients without measurable serum and urine M protein levels: the difference between involved and uninvolved FLC levels (absolute increase must be <math>>10</math> mg/dL)

• Only in patients without measurable serum and urine M protein levels and without measurable disease by FLC levels, bone marrow plasma cell percentage (absolute % must be <math>>10\%</math>)

• Definite development of new bone lesions or soft tissue plasmacytomas or definite increase in the size of existing bone lesions or soft tissue plasmacytomas

• Development of hypercalcemia (corrected serum calcium <math>>11.5</math> mg/dL) that can be attributed solely to the plasma cell proliferative disorder

Source: Rajkumar, et al. Blood 2011;117(18):4691-5.

All response categories (CR, sCR, VGPR, PR, and PD) require 2 consecutive assessments made at any time before the institution of any new therapy; complete response and PR and SD categories also require no known evidence of progressive or new bone lesions if radiographic studies were performed. VGPR and CR categories require serum and urine studies regardless of whether disease at Baseline was measurable on serum, urine, both, or neither. Radiographic studies are not required to satisfy these response requirements. Bone marrow assessments need not be confirmed. For progressive disease, serum M-component increases of  $\geq 1$  g/dL are sufficient to define relapse if starting M-component is  $\geq 5$  g/dL.

1 Note clarifications to IMWG criteria for coding CR and VGPR in patients in whom the only measurable disease is by serum FLC levels: CR in such patients a normal FLC ratio of 0.26-1.65 in addition to CR criteria listed above. VGPR in such patients requires in addition a  $>90\%$  decrease in the difference between involved and uninvolved free light chain FLC levels.

2 Note clarifications to IMWG criteria for coding PD: Clarified than bone marrow criteria for progressive disease are to be used only in patients without measurable disease by M protein and by FLC levels. Clarified that “25% increase” refers to M protein, FLC, and bone marrow results, and does not refer to bone lesions, soft tissue plasmacytomas, or hypercalcemia. Note that the “lowest response value” does not need to be a confirmed value.

The Investigator's assessment of disease response will be used for patient management during the study.

Confirmation of responses should be obtained for biochemical markers but is not necessary for bone marrow or imaging studies. The confirmatory tests should be performed by Day 130. The response date is not the date of confirmation but the initial date when the assessment met the end point. In other words, the second test is confirmatory. If the result is not confirmed by a second evaluation, the status is either non-evaluable and the prior disease status remains valid.

### 9.3.6. Independent Review Committee

An Independent Review Committee (IRC) will be established under the direction of the Sponsor to provide an objective, unbiased, independent review of objective response, using the IMWG criteria (Table 6), as demonstrated based on the pertinent clinical data from the study.

A formal, written IRC charter will be established outlining the composition of the IRC, the data to be evaluated, and the manner of committee meetings.

#### **9.4. Pharmacokinetics**

Serial blood samples for PK analysis will be collected after each tinostamustine dose according to the schedule in [Table 1](#). Blood samples for PK assessment should be collected following the 15-minute supine, resting periods described for the continuous Holter recordings. PK samples are to be collected from the arm opposite of that used for tinostamustine administration.

The calendar date and exact 24-hour clock time of blood sample collection for PK assessments will be documented in the source document and the eCRF.

Samples will be collected, labelled, stored and shipped as detailed in the Laboratory Manual.

## **10. STATISTICAL ANALYSES**

### **10.1. Statistical Basis for Sample Size**

Across both Phases 1 and 2 of the study, a total of up to ~86 patients may be enrolled.

A formal sample size determination/power calculation was not performed for the first phase of the study. Based on experience from previously published similar studies, a total number of 9 (minimum) to 12 (maximum) patients in the dose escalation stage of the study are foreseen.

For Phase 2 of the study, superiority testing will be performed to investigate the null hypothesis that the primary endpoint of responder rate is below or equal to the gold standard against the alternative hypothesis that it is higher than the gold standard. The gold standard is assumed to be 77.5% and a one-sided chi-square test will be performed at the 2.5% level of significance. For power considerations, the alternative working hypothesis is that the responder rate for the study treatment is at least 90%.

In the methodology proposed by Simon ([Simon, 1989](#)), a Phase 2 design can be represented by 4 numbers: N1, R1, N, and R. N1 is the sample size in the first stage. R1 is the critical value in the first stage. If R1 or fewer responses occur in the N1 patients, the study treatment is rejected. N is the combined sample size for both the first and second stages. R is the critical value in the combined sample. If R or fewer of the N patients respond, the study treatment is rejected at the end.

The design is found with PASS Sample Size Software through an exhaustive search of all possible designs (combinations of R1, N1, R and N) that control alpha (0.025) and beta (0.20, meaning power is 0.80). With the minimax approach, the design is selected that has the lowest N.

Per the minimax design, 31 patients are to be enrolled in Stage 1. If >25 of 31 patients (in the FAS) in Stage 1 experience a response to treatment, then enrollment will continue into Stage 2, with up to 40 patients planned to be enrolled. However, if  $\leq 25$  patients in Stage 1 experience a response to treatment, no further patients will be enrolled (in the ongoing Stage 2 recruitment). Thus, a total of up to 71 patients will be enrolled in Phase 2.

If the total number of patients who experience a response is  $\geq 62$  of 71, then the study is considered a success.

### **10.2. Statistical and Analytical Plan**

An overview of the statistical methodology to be employed is provided in the following subsections. Details regarding the statistical methodology will be documented in a formal Statistical Analysis Plan (SAP) prior to database lock.

### **10.2.1. General Methods**

Statistical analyses will be primarily descriptive in nature. Statistical hypothesis testing is neither intended nor appropriate within this context except for the primary endpoint. Confidence intervals will be based on asymptotic methods.

Continuous variables will be summarized using descriptive statistics (n, mean, standard deviation, median, minimum, and maximum). Categorical variables will be summarized showing the number and percentage (n, %) of patients within each classification.

Dependent of the specific analysis, the analysis sets as defined in Section 10.2.2 will be taken from the cohort for Phase 1, for Phase 2 (RP2D) or both phases pooled. Unless specified otherwise below, this will be further defined in the SAP.

### **10.2.2. Analysis Populations**

All patients who receive tinostamustine will be included in the safety set.

All patients in the safety set who had at least one post-ASCT response evaluation will be included in the full analysis set (FAS).

All patients in the FAS with no major protocol deviations will be included in the per-protocol (PP) set.

All patients in the safety set with at least one quantifiable pre-dose and one quantifiable post-dose PK plasma concentration will be included in the PK set.

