**Table 1: Schedule of Events (Phases 1 and 2)**

Procedure	Screening	Conditioning	ASCT	Post-ASCT Follow-up 			
	D-28 to -1	D-1	D0	M1	M2	D100 (±7 days)	D130 (±7 days)
Written informed consent 	X						
Eligibility review	X		X				
Demographics	X						
Medical history	X						
HCT-CI	X						
Cancer history, including history of prior ASCT and other treatments	X						
ECHO or MUGA scan	X						
Pulmonary function testing 	X						
Infectious disease screening 	X						
Pregnancy test 	X						
ECOG performance status	X		X	X	X	X	
Complete physical examination	X						
Targeted physical examination		X	X	X	X	X	
Height	X						
Weight	X		X	X	X	X	
Vital signs 	X	X	X 	X	X	X	
Continuous Holter monitoring		X 					
12-lead ECG 	X 	X 		X			
Hematology 	X	Repeat daily until hospital discharge					
Kidney function tests (creatinine, urea, and uric acid)		Daily from the start of tinostamustine through Day 3 post-ASCT					

*CONFIDENTIAL*

Procedure	Screening	Conditioning	ASCT	Post-ASCT Follow-up 			
	D-28 to -1	D-1	D0	M1	M2	D100 (±7 days)	D130 (±7 days)
Clinical chemistries 	X	X	X	X	X	X	
Coagulation parameters: PT and/or INR, aPTT	X		X	X		X	
Urinalysis 	X						
Tinostamustine administration 		X					
PK sample collection		X 					
ASCT 			X				
Disease assessments							
Skeletal survey 	X						
Bone marrow aspirate and biopsy 	X					D100 (±7 days) 	
Serum / urine M protein quantitation	X			X	X	X	X
Immunoglobulin quantitation (IgA, IgG, and IgM [required]; IgD, IgE [optional])	X			X	X	X	X
Free light chain analysis	X			X	X	X	X
Disease response assessment 	X			X	X	X	
Evaluation for MRD-N						D100 (±7 days) 	
AE monitoring 	AEs, including SAEs, are to be documented from the provision of written informed consent through Day 100.						
Prior/concomitant medications 	All medications administered within 28 days before Day 1 through Day 100 are to be documented.						

1. Patients will be evaluated daily on an inpatient basis until engraftment criteria are met and the patient is discharged from the hospital. Thereafter, study center visits will be performed on an outpatient basis. Visit M1: D30 (±5days); visit M2: D60 (±5days)

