### **3.2.2. Safety**

The safety endpoint in Phase 1 of the study is:

- DLTs

Additional safety endpoints in both Phases 1 and 2 of the study are:

- Incidence of neutrophil and platelet engraftment failure.
- Duration of cytopenia (i.e., absolute neutrophil count [ANC]  $\leq 0.5 \times 10^9/L$ ; platelet count  $\leq 20 \times 10^9/L$ ).
- Cumulative incidence of treatment-related mortality (TRM).
- Transplant-related non-hematologic Grade 3 toxicity over time through Day 30, stratified by hematopoietic cell transplantation comorbidity index (HCT-CI).
- Incidence of adverse events (AEs) and serious adverse events (SAEs).
- Change from baseline in standard safety hematology and clinical chemistry test results.

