### **10.2.3. Missing Data**

Analyses will be based on observed data only; no data will be imputed.

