#### **10.2.8. Efficacy Analyses**

Superiority testing will be performed on FAS in the Phase 2 cohort to investigate the null hypothesis that the primary endpoint of responder rate is below or equal to the gold standard against the alternative hypothesis that it is higher than the gold standard. The gold standard is assumed to be 77.5% (CIBMTR report, December 2017) and a 1-sided 2-step chi-square test will be performed at the 2.5% level of significance for FAS.

For the primary endpoint, also an upper 1-sided 97.5% confidence interval will be calculated for FAS in addition to summary statistics.

For the primary endpoint in other sets and for the secondary endpoints of other responder rates in the FAS, also 2-sided 95% confidence intervals will be calculated in addition to summary statistics.

Response assessments as determined by the Investigator and IRC will be compared, with agreement determined by Kappa coefficient.

Disease assessment variables and their changes from baseline will be summarized visit wise.

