#### **10.2.11. Interim Analyses**

In Phase 2 of the study, at the completion of the Stage 1 with 31 patients, an interim analysis will be performed using the FAS for the Phase 2 cohort to determine whether enrollment will continue in Stage 2. If  $>25$  of 31 patients in Stage 1 experience a response to treatment, then enrollment will continue in Stage 2, with up to 40 patients planned to be enrolled. However, if  $\leq 25$  patients in Stage 1 experience a response to treatment, no further patients will be enrolled in the ongoing Stage 2 recruitment.

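### Does leaving treated patients without a post-transplant response evaluation out of the Phase 2 full analysis set require a change to the plan?

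*Protocol*

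**What the plan says.** The safety set is everyone given tinostamustine. The full analysis set (FAS) adds a condition (Protocol 10.2.2): "All patients in the safety set who had at least one post-ASCT response evaluation will be included in the full analysis set (FAS". The SAP repeats it in section V.I.2. On missing data, Protocol 10.2.3 states: "Analyses will be based on observed data only; no data will be imputed". The first scheduled post-transplant response evaluation is the Month 1 visit; footnote 1 of Table 1 reads "Visit M1: D30 (±5days); visit M2: D60 (±5days".

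The FAS carries the Phase 2 decisions. Section 10.2.8 says "Superiority testing will be performed on FAS in the Phase 2 cohort", and section 10.2.11 says "an interim analysis will be performed using the FAS for the Phase 2 cohort". Section 10.1 sets the continuation rule as more than 25 of "31 patients (in the FAS) in Stage 1 experience a response to treatment" and declares success at 62 or more responders out of 71. The same section treats 71 as an enrolment figure: "Thus, a total of up to 71 patients will be enrolled in Phase 2". Section 6.1 provides for replacement only when a patient was not given tinostamustine followed by transplant.

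The SAP then changes the picture. Section I.C reports that the study was halted on safety signals and later discontinued, and that the Phase 2 primary and secondary objectives and endpoints will not be examined. Section V.F has no interim analysis, section V.G marks test sizes as not applicable, and section VII limits efficacy output to displaying and listing response assessments.

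**The concern.** The condition for entering the FAS depends on outcome. Someone who dies of the regimen or withdraws in the first month never has a response evaluation, so the patients removed are those most likely to be failures. The protocol foresees such events: among its safety endpoints (section 3.2.2) is "Cumulative incidence of treatment-related mortality (TRM". With no rule counting these patients as non-responders, early toxicity would raise the apparent response rate of a single-arm trial judged against a fixed benchmark.

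The decision rule is also loose. Section 10.1 uses 31 both as a number enrolled and as a number in the FAS, gives 71 as enrolled, and does not name the set to which 62 of 71 applies. Nothing says what happens if the FAS falls below 31 or 71. The chi-square test on the FAS in section 10.2.8 and the fixed count in section 10.1 agree when everyone is evaluated, but they can disagree once patients are lost. At stake would be a claim of superiority over 77.5% that the all-treated data do not support.

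**Working it through.** **Inputs.** From Protocol 10.1: null rate 0.775, alternative 0.90, one-sided level 0.025, power 0.80; Stage 1 of 31, continue if more than 25 respond; total 71, success at 62 or more. The share *d* of treated patients with no response evaluation is not in the documents. I assume 1%, 2%, 3% and 5%, and that all of them are non-responders.

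**1. The plan's own design.**

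P(success | p) = Σ over x = 26 to 31 of Bin(x; 31, p) × P[Bin(40, p) ≥ 62 − x]

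At p = 0.775 this is 0.0248; at p = 0.90 it is 0.803. An exhaustive minimax search returns the same design. The stated figures reproduce.

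**2. Effect on the estimate.** If the all-treated rate is 0.775, the FAS rate is 0.775/(1 − d). For example, 0.775/0.95 = 0.816.

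**3. Effect on the decision, by reading.** The chi-square statistic on a FAS of size m with x responders is z = (x/m − 0.775)/√(0.775 × 0.225/m), with success at z ≥ 1.96. I keep the Stage 1 count at more than 25, treat 31 and then 40 patients, and set m to 71 minus those excluded. Responders, excluded patients and evaluated non-responders follow an exact trinomial.

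| d | FAS rate when the all-treated rate is 77.5% | Type I error: counts 26 and 62 among 31 and 71 treated | Type I error: chi-square on reduced FAS, 77.5% all-treated | Type I error: chi-square on reduced FAS, 77.5% evaluable-only |
|---|---|---|---|---|
| 1% | 78.3% | 0.0248 | 0.027 | 0.019 |
| 2% | 79.1% | 0.0248 | 0.032 | 0.016 |
| 3% | 79.9% | 0.0248 | 0.042 | 0.015 |
| 5% | 81.6% | 0.0248 | 0.071 | 0.013 |

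The count column is constant because, with 71 treated, an excluded patient cannot contribute a response and so acts as a non-responder. The last column takes the true responder rate among all treated as 0.775(1 − d), so that the benchmark and the FAS have the same kind of denominator.

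**4. Where the two rules part.** The smallest number of responders that passes the chi-square test is 62 for m = 71, 62 for m = 70, 61 for m = 69 and 60 for m = 68. One exclusion changes nothing; two can. With 61 responders:

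- m = 71: 61/71 = 85.9%, z = 0.0842/0.0496 = 1.70, fails.
- m = 69: 61/69 = 88.4%, z = 0.1091/0.0503 = 2.17, passes.

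**5. What the SAP still does with the FAS.** Set against each use of the FAS in the protocol:

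- Stage 1 continuation and interim (Protocol 10.1, 10.2.11): SAP V.F plans no interim.
- Superiority test (Protocol 10.2.8): SAP I.C drops the Phase 2 endpoints and V.G has no test size.
- Response rate: SAP VII displays investigator and independent-committee assessments and lists response variables as recorded. No rate is tested or compared with 77.5%.
- Remaining uses: the table in SAP V.I still assigns efficacy to the FAS, and VI.C counts how many patients fall in each set. Both are descriptive.

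Early deaths and withdrawals stay visible elsewhere. Disposition (SAP VI.B) uses enrolled patients as its denominator, and adverse events (SAP VIII) are summarised for the Safety Population.

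**The case for a change.** The strongest case for a change is that the text still stands. SAP III.C repeats the superiority test and the 62-of-71 rule, V.I.2 keeps the FAS definition, and a later trial that borrowed this design would inherit the fault. The remedy looks cheap: use all treated patients, count those without an evaluable Day 100 response as failures, and keep the present FAS for sensitivity. Type I error would then be 0.0248 at any *d* against an all-treated 77.5%, and lower against an evaluable-only one.

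Much of that stands. The exclusion is tied to outcome, the set for 62 of 71 is not named, and a patient evaluated only at Day 30 enters the FAS with no Day 100 status and no rule to assign one. Anyone reusing the Phase 2 design should settle these points first.

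Two parts do not carry over to this trial. First, no document proposes reusing the design, and the harm is conditional even if Phase 2 had run. It needs the chi-square reading rather than the count rule, an appreciable *d*, and a benchmark computed on all treated patients. The 77.5% comes from a registry report, and the available text does not give its denominator. Second, the remedy is not free. If the 90% alternative refers to evaluable patients only, the all-treated rate is 0.90(1 − d), and power with the same thresholds falls from 0.80 to 0.73, 0.64, 0.55 or 0.38 for *d* of 1%, 2%, 3% or 5%. The bases of 77.5% and 90% would have to be fixed before the denominator is chosen.

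**Conclusion.** The wording gap is genuine, but no change to the plan follows, because a change would gain nothing. Every inferential use of the FAS belonged to Phase 2, and the SAP has withdrawn Phase 2, its interim analysis and its test. What remains is a display and listing of responses and a count of patients in each set, and no conclusion hangs on either.

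Had Phase 2 gone ahead, the size of the problem would have depended on the reading: none under the count rule with 71 treated (0.0248), and 0.027 to 0.071 under a chi-square test on a reduced FAS. That range assumes 1% to 5% excluded, all of them non-responders, and an all-treated 77.5%. With an evaluable-only benchmark, the same test stays below 0.025. Protocol 10.2 left statistical detail to the SAP, where these rules would normally have been completed; discontinuation made that unnecessary.
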